LIST OF ACRONYMS AND ABBREVIATIONS

Abbreviation	Definition
ACC	American College of Cardiology
ACE	Angiotensin Converting Enzyme
AE	Adverse Event
AHA	American Heart Association
ALP	alkaline phosphatase
ALT	alanine aminotransferase
ANCOVA	Analysis of Covariance
ARB	Angiotensin II Receptor Blocker
AST	aspartate aminotransferase
AUC _{inf}	Area under (concentration-time) curve to infinity
AUC _{last}	Area under (concentration-time) curve to last time-point
BNP	Brain natriuretic peptide
BP	Blood pressure
BUN	Blood urea nitrogen
C	Celsius
CEC	Clinical Endpoints Committee
CEO	Chief Executive Officer
C _{ave}	Average plasma concentration over 24 hours
C _{max}	Maximum observed plasma concentration
C _{min}	Minimum observed plasma concentration
CNS	Central nervous system
COX-2	cyclooxygenase-2
CPK	creatin phosphokinase
CRF	Case Report Form
DCC	Direct Current Cardioversion
DSMB	Data Safety Monitoring Board
ECG	Electrocardiogram
eGFR	estimated glomerular filtration rate
ESV	End systolic volume
F	Fahrenheit
FAS	Full Analysis Set
GCP	Good Clinical Practice
GGT	gamma glutamyl transferase
GLP	Good Laboratory Practice
GRAS	Generally Regarded as Safe
HDPE	High density polyethylene
hERG	human ether-à-go-go-related gene
HIV	Human Immunodeficiency Virus
HPMC	Hydroxypropyl methylcellulose
hsCRP	high sensitivity C-reactive protein
IB	Investigator's Brochure
ICH	International Conference on Harmonisation
ID	Identification
IEC	Independent Ethics Committee

Cardiology Department, HNELHD
Clinical Trial Protocol: PRESSURE-AF

Version: 1.4
Date: 24/11/2020

IP	Investigational product
ITT	Intent-to-Treat
IUD	Intrauterine device
IV	Intravenous
IWRS	Interactive web response system
kg	Kilogram
LDH	lactate dehydrogenase
LS Mean	Least Squares Mean
LV	Left ventricular
LVEDVi	Left ventricular end diastolic volume (indexed)
LVEF	Left ventricular ejection fraction
LVESVi	Left ventricular end systolic volume (indexed)
MACCE	Major cardiac and cerebrovascular events
MAD	Multiple ascending dose
mg	milligram
MI	Myocardial infarction
min	Minute
mITT	Modified Intent to Treat
mL	Millilitre
MMRM	mixed model repeated measures
MTD	maximum tolerated dose
nM	nanomols
NOAEL	No observed adverse effect level
NSAID	non-steroidal anti-inflammatory drug
NT-proBNP	Brain natriuretic peptide type B
NYHA	New York Heart Association
PAD	Pharmacologically active dose
PCEs	polychromatic erythrocytes
PCI	Percutaneous coronary intervention
pg	picogram
PI	Principal Investigator
PICF	Participant Information and Consent Form
PK	Pharmacokinetic
PP	Per Protocol
PPP	PharmPackPro
PSA	Prostate specific antigen
PT	prothrombin time
PTT	partial thromboplastin time
QTc	Corrected QT interval
QTcB	Bazzet's corrected QT interval
RBC	Red blood cell
SAD	single ascending dose
SAE	Serious Adverse Event
SAP	Statistical Analysis Plan
SC	Steering Committee
SOP	Standard Operating Procedure
SRM	Study Reference Manual
STEMI	ST elevation myocardial infarction

CONFIDENTIAL

Page 9 of 21

Cardiology Department, HNELHD
Clinical Trial Protocol: PRESSURE-AF

Version: 1.4
Date: 24/11/2020

T _{1/2}	Terminal elimination half-life
TK	Toxicokinetic
T _{max}	Time to maximal concentration
ULN	Upper limit of normal
uM	micromol
WBC	White blood cell
WOCBP	Woman of child-bearing potential

Cardiology Department, HNELHD
Clinical Trial Protocol: PRESSURE-AF

Version: 1.4
Date: 24/11/2020

1. BACKGROUND AND RATIONALE

1.1. ATRIAL FIBRILLATION AND DIRECT CURRENT CARIOVERSION

Chest pressure during direct current cardioversion for atrial fibrillation is often utilised when patients fail regular cardioversion, often as standard of care. We hypothesise that the routine use of chest pressure for direct current cardioversion will be safe and reduce energy use compared to direct current cardioversion without pressure for atrial fibrillation.

There are numerous potential advantages to identifying the benefit of chest pressure for direct current cardioversion. This would result in potential improved cardioversion success, decreased energy use, potentially lower post procedural pain and decreased duration of anaesthetisation for patients.

1.2. CLINICAL STUDIES OF DIRECT CURRENT CARIOVERSION FOR ATRIAL FIBRILLATION

There have been numerous studies, mostly observational and retrospective, examining the success of cardioversion in atrial fibrillation, however none have examined the role of chest pressure in cardioversion success. (1, 2)

1.2.1. Safety

Direct current cardioversion requires anaesthetic support for sedation as well as three weeks of therapeutic anticoagulation prior. The major complications from direct current cardioversion including ischaemic stroke (<1%) and ventricular arrhythmias due to non-synchronised shock. (2)

1.2.2. Efficacy

A retrospective review of 12 months of cardioversions for atrial fibrillation at our centre was performed, with a total of 147 patients. The success of the first and last shocks for reversion of sinus rhythm were 71% and 87% respectively.

1.3. STUDY RATIONALE

The success of direct current cardioversion relies on the delivery of energy to the heart. Most of the energy is displaced laterally across the chest wall, with only a small proportion delivered to the heart. (2) Chest pressure reduces transthoracic resistance by 25%, increasing cardiac energy delivery. (3) Therefore, routine chest compression may improve the success rate and decrease overall energy use.

Biphasic energy will be utilised due to reported increased efficacy and less myocardial stunning compared to monophasic cardioversion. (4, 5) Three weeks of therapeutic anticoagulation will be required prior to cardioversion in keeping with international guidelines or transoesophageal echocardiography excluding left atrial appendage thrombus. (6) 150 joules shall be used as the initial energy given guideline recommendations for starting energies between 100 and 200 joules. (7, 8) Cardioversion will be timed to end-expiration to maximally reduce transthoracic impedance. (9)

Cardiology Department, HNELHD
Clinical Trial Protocol: PRESSURE-AF

Version: 1.4
Date: 24/11/2020

2. STUDY OBJECTIVES

To evaluate the efficacy of chest pressure for direct current cardioversion in AF.

2.1. PRIMARY OBJECTIVE

To assess the efficacy of chest pressure for direct current cardioversion in atrial fibrillation.

2.2. SECONDARY OBJECTIVES

To confirm safety and tolerability of chest pressure for the proceduralist

2.3. OVERALL TRIAL DESIGN

This is a multi-centre, randomised controlled study to assess the efficacy, and safety of direct current cardioversion for atrial fibrillation. Participants will be screened on the day of direct current cardioversion. Consenting participants will be randomised 1:1 to have an initial strategy of chest pressure with cardioversion or an initial cardioversion without chest pressure.

2.4. NUMBER OF PARTICPANTS

It is planned that approximately 308 adult participants aged over 18 years (inclusive) will participate in the study.

2.5. STUDY PERIOD/DURATION OF PARTICIPANT PARTICIPATION

The duration of the study for each participant is the day of the procedure.

It is anticipated that recruitment will take approximately 24 months. The study period is expected to be 2021-2023.

2.6. PARTICIPANT SELECTION AND WITHDRAWAL

2.6.1. Trial selection record

Investigators must keep a record of participants who were considered for the study but were not enrolled.

2.6.2. General considerations

Only participants who meet all the inclusion and none of the exclusion criteria will be eligible to participate in the study.

2.6.3. Inclusion criteria

1. Aged over 18 years of age.
2. Have Atrial Fibrillation.
3. Are referred for direct current cardioversion for atrial fibrillation.
4. Three weeks of therapeutic anti-coagulation prior to cardioversion or transoesophageal echocardiography excluding left atrial appendage thrombus.

2.6.4. Exclusion criteria

- Pregnant or breastfeeding females.
- Inability to provide informed consent.
- Medical comorbidity where anticoagulation is contra-indicated.

Cardiology Department, HNELHD
Clinical Trial Protocol: PRESSURE-AF

Version: 1.4
Date: 24/11/2020

2.6.5. Concomitant Medications

Any medications taken must be documented in the participant notes. This record should include the drug name, the dose and frequency, route of administration and the indication.

2.6.6. Withdrawal of Participants from Study

Participants can terminate their study participation at any time and without giving a reason, without prejudice to further treatment. Participants who discontinue from the trial should always be asked about the reason(s) for their discontinuation and about the presence of any AEs. AEs should be followed up until resolved or stable and determined to be chronic.

The Investigator or treating physician can exclude a participant from continuing in the trial.

Possible reasons for discontinuing a participant may include:

- Participant withdrawal of consent.
- Any unacceptable AEs, in the judgement of the Investigator.
- Participant non-compliance with the protocol.

2.7. STUDY TREATMENTS

2.7.1. Description of the control arm

Patients in the control arm will receive sequential shocks of 150J without pressure, 200J without pressure, 360J without pressure and 360J with chest pressure until cardioversion success or four shocks have been provided. The cardioversion will be performed under intravenous sedation guided by an anaesthetist (Propofol ± midazolam weight-based dosing and titrated to effect).

2.7.2. Description of intervention arm

Patients in the intervention arm will receive sequential shocks of 150J with pressure, 200J with pressure and two shocks at 360J with pressure until cardioversion success or four shocks have been provided. The cardioversion will be performed under intravenous sedation guided by an anaesthetist (Propofol ± midazolam weight-based dosing and titrated to effect).

2.7.3. Chest pressure standardisation

The application of standardised chest pressure is needed to ensure consistency of the intervention. A review of chest pressure provided by Cardiology Advanced Trainees (the proceduralists for the intervention) was performed. Of thirty-six measurements, on a single set of scales, between four advanced trainees (8 measurements each), an average of 25.5±2.6 kilograms of chest pressure was provided.

2.7.4. Anaesthetic Protocol for DC Cardioversion

Anaesthetic agents have potential pro and antiarrhythmic effects. (9, 10) As such, the standardisation of anaesthetic provision will be necessary for internal validity of the trial. Generally, the application propofol and midazolam is routinely used for elective direct current cardioversion. During this trial, the weight-based dosing of propofol +/- midazolam, titrated to effect, will be used for sedation purposes.

2.7.5. Method of assigning participants to treatment group

Participant eligibility will be established before randomisation. Eligible participants who consent to involvement will be assigned to either the control or intervention arm in a 1:1 ratio. Patients will be

Cardiology Department, HNELHD
Clinical Trial Protocol: PRESSURE-AF

Version: 1.4
Date: 24/11/2020

randomised via a randomisation app. This app, given to all researchers, will provide synchronised information about patient allocations.

3. STUDY PROCEDURES

3.1. PARTICIPANT INFORMATION

The Investigator must provide adequate information regarding the study conduct and obtain written informed consent from the participant before any tests or investigations outlined in the study protocol are carried out.

3.2. DAY OF CARDIOVERSION

On the day of cardioversion the following will be performed:

- Review eligibility criteria.
- Record participant medical history and medications.
- Record the height and weight of the patient.
- Vital signs (see Section 5.2).
- 12-lead ECG.
- Written informed consent.
- Upon confirmation of eligibility and consent to proceed, participants will be randomised.

The protocol for DC cardioversion (control or intervention) will then be performed based on randomisation. After the DC cardioversion is completed, the following will be performed:

- Chest pain 30 minutes post procedure will be recorded (0-10 ordinal scale)
- Record of post-procedural complications:
 - shock provided to proceduralist

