Cardiology Department, HNELHD
Clinical Trial Protocol: PRESSURE-AF

Version: 1.4
Date: 24/11/2020

Study Title:	Investigating the Efficacy of Chest Pressure for Direct Current Cardioversion in Atrial Fibrillation: A Randomised Control Trial (Pressure-AF)
Protocol Number:	2020/ETH02116
CTN Number:	ACTRN12620001028998p
Intervention	Chest Pressure
Indication:	Direct Current Cardioversion for Atrial Fibrillation
Study Design:	Investigator-initiated
Version:	1.4
Date:	24th November 2020

CONFIDENTIAL

Cardiology Department, HNELHD
Clinical Trial Protocol: PRESSURE-AF

Version: 1.4
Date: 24/11/2020

PROTOCOL SYNOPSIS

Study Title:	Investigating the Efficacy of Chest Pressure for Direct Current Cardioversion in Atrial Fibrillation: A Randomised Control Trial (Pressure-AF)
Study Period:	2021-2023
Hypothesis	The routine use of manual chest pressure for direct current cardioversion in atrial fibrillation will result in decreased energy requirements and will prove safe for patient and proceduralist.
Objectives:	
Primary objective:
 
• To assess the efficacy of chest pressure for direct current cardioversion in atrial fibrillation. 
The secondary objectives are:
 
• To confirm safety and tolerability of chest pressure for patient and proceduralist
Study Plan	
This is a multi-centre, randomised, single blinded trial of chest pressure for direct current cardioversion in atrial fibrillation.
 
Participants will be screened from all participants referred for cardioversion for atrial fibrillation aged over 18 years of age. Randomisation will occur after consent is obtained and on enrolment into the study.
 
Participants will be randomised to an initial strategy of chest pressure (intervention) or a strategy of chest pressure only if refractory to cardioversion without pressure (control).

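### Nothing in the protocol keeps the anaesthetist unaware of the arm while sedation is chosen and titrated, although it calls standardised anaesthesia necessary for internal validity

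*Protocol*

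**What the plan says.** Four parts of the protocol bear on this point.

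- **Order of steps.** Section 3.2 lists the checks on the day and ends with "Upon confirmation of eligibility and consent to proceed, participants will be randomised". It continues: "The protocol for DC cardioversion (control or intervention) will then be performed based on randomisation". The synopsis (Study Plan) agrees: "Randomisation will occur after consent is obtained and on enrolment into the study".
- **Sedation is part of the cardioversion.** Section 2.7.1 says of the control arm: "The cardioversion will be performed under intravenous sedation guided by an anaesthetist". Section 2.7.2 uses the same sentence for the intervention arm.
- **Anaesthesia.** Section 2.7.4 begins "Anaesthetic agents have potential pro and antiarrhythmic effects" and concludes that "the standardisation of anaesthetic provision will be necessary for internal validity of the trial". The rule it then sets is that "the weight-based dosing of propofol +/- midazolam, titrated to effect, will be used for sedation purposes". It gives no criterion for adding midazolam and no target depth.
- **Who sees the allocation.** Section 2.7.5 assigns patients through an app that all researchers hold and that shares allocations among them. The anaesthetist is not mentioned. The synopsis calls the trial single blinded without naming the blinded party.

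**The concern.** Randomisation balances what exists before it. It does not balance a co-intervention chosen afterwards by someone who may know the arm. Here sedation comes after allocation, and the two elements left to judgement (midazolam or not, and how deep) are the ones that could vary with knowledge of the arm. An anaesthetist expecting firm manual pressure on the chest might sedate differently from one who is not.

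On the protocol's own premise that the agents can act on rhythm, such a difference could alter conversion. That would affect total joules (the primary endpoint) and first-shock success. Residual sedation could also affect the pain score at 30 minutes. A difference between arms would then mix the effect of pressure with the effect of sedation, and no later analysis could separate them if the drugs and doses had not been captured. An analysis plan cannot change when the allocation was opened.

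**Working it through.** **1. Does allocation precede sedation?** Section 3.2 places randomisation before the arm-specific cardioversion, and sections 2.7.1 and 2.7.2 make sedation part of that cardioversion. Allocation therefore exists before sedation. This follows from the order of steps; no section lists sedation as a timed step of its own.

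**2. Is the arm concealed from the anaesthetist?** No section blinds the anaesthetist or keeps the allocation closed until sedation is complete. Equally, no section says that the anaesthetist is told the arm before induction.

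**3. What is fixed and what is open?** Agents, intravenous route and weight-based dosing are the same in both arms. The use of midazolam and the depth of sedation are open.

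**4. The plan's own figure.** Inputs from the synopsis (Sample Size): SD 188 J, difference 60 J, two-sided alpha 0.05, power 0.8, 1:1 allocation.

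- n per arm = 2 × (1.960 + 0.842)² × 188² / 60² ≈ 154.1, which rounds up to 155, or 310 in total.
- Power at 154 per arm is 0.7997.

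The stated 308 reproduces within rounding, so the sample size is not in question.

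**5. How far could an imbalance move the primary endpoint?** The documents give no sedation effect. Assume, for illustration only, that arm-dependent sedation shifts first-shock success by 5 percentage points in one arm.

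- Cumulative energy over the four steps (sections 2.7.1 and 2.7.2): 150; 150 + 200 = 350; 350 + 360 = 710; 710 + 360 = 1070 J.
- Lower end, every shifted patient converts at the second shock: 0.05 × (350 − 150) = 10 J.
- Upper end, every shifted patient goes through all four shocks: 0.05 × (1070 − 150) = 46 J.
- Middle value from the retrospective review. Inputs: mean 280 J (synopsis) and first-shock success 71% (section 1.2.2), treated as the same series, with an assumed historical first shock of 150 J. Mean energy among first-shock failures = (280 − 0.71 × 150) / 0.29 = 173.5 / 0.29 ≈ 598 J. The shift is then 0.05 × (598 − 150) ≈ 22 J.

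**6. What would a spurious shift do to the test?** The standard error of the arm difference is 188 × √(2/154) = 21.4 J. With no true effect of pressure and a bias of b joules, the two-sided rejection rate is Φ(−1.96 + b/21.4) + Φ(−1.96 − b/21.4).

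| Assumed bias b (J) | Rejection rate |
|---|---|
| 0 | 5.0% |
| 5 | 5.6% |
| 10 | 7.5% |
| 20 | 15.4% |
| 30 | 28.8% |

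These are consequences of assumed shifts, not estimates of a shift.

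**The case against.** The strongest reply is that the documents show sequence, not disclosure. A reader might infer that the anaesthetist sedates knowing the arm. The protocol does not say so: the app goes to researchers, the anaesthetist is not named among them, and knowledge at induction would depend on local practice. This stands, and it limits the point to an absence of protection.

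A reader might also infer that nothing about the anaesthesia is standardised. That goes too far, because agents, route and weight-based dosing are specified identically for both arms. What stands is that the remaining discretion has no criterion.

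A third tempting inference is that the awake patient is unblinded while the team prepares. The protocol never says that the patient is the blinded party and describes no arm-specific preparation before the shock, so the text does not support it.

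On size, the 5-point shift has no source in the documents and no direction is argued. The 46 J end requires every affected patient to go through all four shocks. Section 1.2.2 reports 71% success at the first shock and 87% at the last, so 16 of every 29 first-shock failures (55%) converted later. The 22 J figure is the more reasonable illustration, but still only an illustration.

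On recording, section 2.6.5 already requires medications, with dose and route, in the participant notes. It does not name sedatives or place them on the CRF, so the gap is partial.

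Finally, the anaesthetist is most likely to learn the arm after the first shock, when pressure or its absence is visible. Delayed allocation cannot prevent that, and total joules accumulate over those later shocks. This stands as a limit on the remedy.

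**Conclusion.** The point holds as an unguarded route to bias. The protocol says that standardised anaesthesia is needed for internal validity, leaves midazolam use and depth open, places allocation before sedation, and has no provision to keep the anaesthetist unaware of the arm. That the anaesthetist actually knows the arm, or sedates differently because of it, is not shown.

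Neither the size nor the direction of any bias can be found from the documents. The range of 10 to 46 J, with about 22 J as the middle value, rests on the assumed 5-point shift. The middle value also assumes a 150 J historical first shock and a single retrospective series behind the mean and the 71%. Against a 60 J target and a standard error of 21.4 J, shifts of that order would matter if they occurred. The stated sample size is unaffected. This is a cheap improvement, not a defect that invalidates the design.

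**What to change.** - In sections 3.2 and 2.7.5 and in the synopsis (Study Plan), keep consent and eligibility where they are. State that the app allocation is opened only after the anaesthetist confirms that sedation is established, immediately before the first shock. The synopsis must change as well, because it ties randomisation to enrolment and would otherwise contradict the amended section 3.2.
- Add CRF fields for sedative and analgesic drugs and total doses, and tabulate them by arm. This makes any imbalance visible, including one from top-up sedation.

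No agent, dose or clinical rule changes.

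The cost is a few sentences, one or two CRF fields and a few seconds more under sedation. Section 1.1 names shorter anaesthesia as a possible benefit, so the delay should be kept to opening the app. The operator learns the arm only moments before the first shock, and top-up sedation between shocks remains unblinded.

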4. TRIAL ENDPOINTS

4.1. EFFICACY ENDPOINTS

4.1.1. Primary

- Total joules provided to patient.

4.1.2. Secondary

- First shock success in reversion to sinus rhythm
- Transthoracic impedance at the time of shock
- Sinus rhythm at post cardioversion ECG

4.2. SAFETY AND TOLERABILITY ENDPOINTS

- Chest pain 30 minutes post procedure.
- Shock to proceduralist

Cardiology Department, HNELHD
Clinical Trial Protocol: PRESSURE-AF

Version: 1.4
Date: 24/11/2020

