Number of participants:	
It is planned that 308 participants will be randomised in a 1:1 ratio to one of two treatment arms:
 
• 154 will undergo standard direct current cardioversion.
➤ 1 shock – 150 Joules without chest pressure➤ 1 shock – 200 Joules without chest pressure➤ 1 shock – 360 joules without chest pressure➤ 1 shock – 360 joules with chest pressure• 154 will undergo an initial strategy of chest pressure.
➤ 1 shock – 150 Joules with chest pressure➤ 1 shock – 200 Joules with chest pressure➤ 1 shock – 360 Joules with chest pressure➤ 1 shock – 360 joules with chest pressure
Key inclusion	Participants who:

CONFIDENTIAL

Cardiology Department, HNELHD
Clinical Trial Protocol: PRESSURE-AF

Version: 1.4
Date: 24/11/2020

- criteria:
- Aged over 18 years of age.
 - Have Atrial Fibrillation.
 - Are referred for direct current cardioversion for atrial fibrillation.
 - Three weeks of therapeutic anti-coagulation prior to cardioversion or transoesophageal echocardiography excluding left atrial appendage thrombus.
- Key exclusion criteria:
- Participants with:
- Pregnant or breastfeeding females.
 - Inability to provide informed consent.
 - Other atrial tachyarrhythmias (atrial flutter or multifocal atrial tachycardia)
 - Medical comorbidity where anticoagulation is contra-indicated
- Test strategy:
- Direct current cardioversion for atrial fibrillation with and without chest pressure as the initial strategy.
- Duration of study per participant:
- Day of procedure only.
- Criteria for evaluation:
- Primary efficacy endpoints
- Total joules provided during encounter.
- Secondary efficacy endpoints:
- Success of first shock for reversion to sinus rhythm.
 - Transthoracic impedance at the time of shock.
 - Sinus rhythm at post cardioversion ECG
- Safety and Tolerability Endpoints
- Patient chest pain post cardioversion (Ordinal Scale 0-10).
 - Incidence of shock provided to proceduralist.
- Statistical methods and analyses:
- Analysis Sets
- Full analysis set (FAS) Intention to Treat (ITT) Protocol: All participants randomised into the study. Participants will be analysed according to the intervention to which they were randomised. Efficacy analyses performed in the FAS are considered supportive of analyses performed in the PP set.

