 - Per-protocol (PP) set: All participants from the ITT population who completed the study in compliance with the protocol and who reported no major violation of the study protocol. Participants will be analysed according to the intervention which they received. The final decision to exclude a participant from the PP set will be taken during a blinded data

CONFIDENTIAL

review meeting before database lock. Efficacy analyses performed in the PP set are considered supportive of analyses performed in the ITT set.

Sample Size

A retrospective review of 12 months of direct current cardioversions was performed at our centre. The mean energy provided during an encounter was 280 ± 188 Joules. Assuming a mean reduction of 60 joules in energy in the intervention group (one third of the standard deviation), a total of 308 patients (154 in each arm) would need to be recruited for an alpha of 0.05 and power of 0.8. This has been discussed and confirmed with statisticians at the Hunter Medical Research Institute.

Statistical Analyses

Continuous variables will be reported as mean \pm standard deviation or as median and percentiles if appropriate. Normally distributed variables will be compared using the paired Student's t-test. Otherwise comparisons between both the groups will be performed using the Mann-Whitney U test. Categorical variables will be stated as absolute and relative frequencies and compared using the χ^2 test. All tests are two-tailed. A P-value of <0.05 will be considered as statistically significant.

Sensitivity analyses of the primary endpoint will be performed in the FAS to assess the impact of missing data on the robustness of the primary analysis. The primary analysis will also be repeated in the PP set.

The following secondary endpoints will be analysed and summarised using the methods described for the primary endpoint:

- Success of first shock for reversion to sinus rhythm.
- Average transthoracic impedance.
- Chest pain post procedure – ordinal 0-10 scale.
- Shock provided to the provider.

Successful cardioversion is defined as sinus rhythm 1 minute after cardioversion.

Cardiology Department, HNELHD
Clinical Trial Protocol: PRESSURE-AF

Version: 1.4
Date: 24/11/2020

Table of Contents

PROTOCOL SYNOPSIS	2
LIST OF ACRONYMS AND ABBREVIATIONS	8
1. BACKGROUND AND RATIONALE	11
1.1. ATRIAL FIBRILLATION AND DIRECT CURRENT CARIOVERSION	11
1.2. CLINICAL STUDIES OF DIRECT CURRENT CARIOVERSION FOR ATRIAL FIBRILLATION.....	11

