5.2. SAFETY AND TOLERABILITY

Safety will be assessed by recording of AEs, and MACCE.

- Participants will be questioned and monitored throughout in-patient stay with regard to any AEs they may have experienced. See Section 6 for further details on recording AEs.
- Vital signs will be measured after the participant has been supine for 5 minutes and will include blood pressure (BP), pulse rate, respiratory rate and temperature.
- Measurement of chest pain 30 minutes post procedure will be elicited by medical staff (Ordinal scale of 0-10).
- Shock provided to proceduralist will be documented.

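### The objective is to confirm safety for the proceduralist, but operator shock is given only a test of difference, with no acceptable rate and no confidence interval

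*Protocol*

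**What the plan says.** **Aim.** The synopsis hypothesis is that routine chest pressure "will prove safe for patient and proceduralist". The synopsis objective is "To confirm safety and tolerability of chest pressure for patient and proceduralist", and section 2.2 has "To confirm safety and tolerability of chest pressure for the proceduralist".

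**Endpoint.** Section 4.2 lists "Shock to proceduralist". The synopsis has "Incidence of shock provided to proceduralist", and section 5.2 says "Shock provided to proceduralist will be documented". None of these gives a unit or denominator (per patient, per shock, or per shock with pressure).

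**Analysis.** The synopsis (Statistical Analyses) puts "Shock provided to the provider" on the list of secondary endpoints to be analysed as the primary endpoint is. The synopsis and section 8.2 assign the chi-square test to categorical variables, two-tailed, with significance at P below 0.05. Section 8.3 analyses primary and secondary outcomes by randomised arm. Section 8.5 adds a descriptive summary of safety data by treatment group, with counts and percentages.

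**Exposure.** Control patients receive "150J without pressure, 200J without pressure, 360J without pressure and 360J with chest pressure" (section 2.7.1), stopping at success. In the intervention arm every shock is given with pressure (section 2.7.2).

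**Size.** The 308 patients (154 per arm) are derived from total joules alone. For operator shock the protocol gives no expected rate, margin, acceptable rate or power.

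**The concern.** To confirm safety is to show that a risk is no larger than some acceptable level. A test of difference asks whether the data rule out equality between the arms. When events are rare and the sample was sized for another endpoint, such a test will often be non-significant whether or not a relevant risk exists. The aim and the method therefore do not fit.

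This is more than a detail that an analysis plan could supply later, because the protocol itself names the inferential method for this endpoint. At stake is a stated secondary objective and the operator part of the safety hypothesis. If pressure at every shock were adopted routinely, operators would want to know how large the risk could still be, and the planned test does not answer that.

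**Working it through.** **1. The plan's own figure.** Inputs from the synopsis (Sample Size): difference 60 J, SD 188 J, alpha 0.05 two-sided, power 0.8.

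n per arm = 2 × [188 × (1.960 + 0.842) / 60]² = 154.1

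The stated 154 per arm reproduces (155 if rounded up; power at 154 is 0.80). Operator shock does not enter the calculation.

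**2. What the chi-square test can detect.** With x events among 154 intervention patients and none among 154 controls, the uncorrected Pearson statistic reduces to χ² = 308x / (308 − x). The expected number of events in each arm is x/2. The limits are Clopper-Pearson, two-sided 95%, for x/154.

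| x v 0 | χ² | p, chi-square | p, Fisher | Upper limit for the risk |
|---|---|---|---|---|
| 0 | – | – | – | 2.4% |
| 3 | 924/305 = 3.03 | 0.082 | 0.248 | 5.6% |
| 4 | 1232/304 = 4.05 | 0.044 | 0.123 | 6.5% |
| 5 | 1540/303 = 5.08 | 0.024 | 0.061 | 7.4% |
| 6 | 1848/302 = 6.12 | 0.013 | 0.030 | 8.3% |

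For zero events the limit is 1 − 0.025^(1/154) = 2.4%.

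At three and four events the expected counts are 1.5 and 2 per arm. That is below 5, so the chi-square approximation is poor. Fisher's exact test needs 6 v 0, where the chi-square accepts 4 v 0.

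**3. Power.** The documents give no event rate, so the true risks below are assumptions, per intervention patient, with none in controls. Power is then P(X ≥ 4) for the chi-square and P(X ≥ 6) for Fisher, with X binomial (154, risk).

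| Assumed risk | Chi-square | Fisher |
|---|---|---|
| 1% | 7% | 0.5% |
| 2% | 37% | 9% |
| 3% | 68% | 32% |
| 5% | 95% | 79% |

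At 1%, at least one operator shock would occur with probability 1 − 0.99^154 = 79%, but the test would be significant in only 7% of trials.

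**4. Does the control arm's low exposure cause this?** Section 1.2.2 gives first- and last-shock success of 71% and 87%. If these carry over to the control arm (an assumption), between 13% and 29% of control patients reach shock 4. That is 154 × 0.13 = 20 to 154 × 0.29 = 45 control shocks with pressure, out of about 239 to 288 control shocks (8% to 16%).

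Now assume a risk per pressure shock, and 1.55 to 1.87 shocks per intervention patient (1 + 0.29 + 0.13 + 0.13 to 1 + 0.29 + 0.29 + 0.29).

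| Assumed risk per pressure shock | Chi-square power, control shock 4 counted | Chi-square power, control risk zero |
|---|---|---|
| 1% | 18% to 21% | 22% to 32% |
| 2% | 49% to 54% | 70% to 83% |

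A less exposed control arm raises power. The shortfall comes from rare events and a test without a margin, not from the control arm's low exposure.

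**The case against.** **No decision rule is stated.** A reader might infer from the words confirm and prove that a non-significant result will be declared to be safety. No passage says so. The protocol gives an aim and a generic test and does not connect them by a rule. This stands, and the point is limited to the mismatch between the two.

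**The control arm is a proper comparator.** A reader might argue that the comparison is uninformative because most control shocks are given without pressure. That does not hold. A nearly unexposed group is the right reference for added risk, and step 4 of the working shows that it helps power.

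**Control rescue shocks are not misclassified.** A reader might see an operator shock at control shock 4 as charged to a no-pressure arm. The synopsis defines control as pressure only in refractory patients, and section 2.7.1 makes the fourth shock part of the assigned strategy. Comparing strategies by randomised arm is the trial's question. The arm comparison should stay; it does not, however, give the risk per exposure.

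**Events would not be hidden.** Section 8.5 requires counts and percentages by treatment group, so three shocked operators would appear as 3/154 against 0/154. This stands too. But counts alone do not say how large the risk could still be, and the only inference attached to them is the chi-square.

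**Interval details often sit in an analysis plan.** True of the details. Here, though, the protocol has already assigned a test that cannot meet its objective.

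**Conclusion.** The point holds in a limited form: the only inferential method that the protocol assigns to operator shock cannot confirm safety, and no acceptable rate or interval is given that could. With no control events, up to three shocked operators by chi-square (or five by Fisher's test) would be non-significant, while the risk could still be as high as 5.6% (or 7.4%). A trial with no events at all would exclude only risks above 2.4%.

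The p-values and limits follow from 154 per arm and the stated counts. The power figures rest on assumed event rates, and the exposure figures on carrying over the retrospective success rates. The exact limits treat encounters as independent, although the same operators will perform many of them.

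The primary endpoint is unaffected. This is a low-cost improvement to a secondary safety objective.

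**What to change.** 1. In the synopsis (Statistical Analyses) and section 8.2, remove the chi-square test at P below 0.05 as the criterion for operator shock.
2. Report the proportion of encounters with an operator shock in each randomised arm, and the difference between arms, with exact 95% confidence intervals.
3. Base the safety statement on the upper limit for the intervention arm, judged against an acceptable rate that the investigators state before database lock. Choosing that rate is their decision.
4. As a supporting analysis, report operator shocks per shock delivered with pressure across both arms, including control shock 4. Use an interval that allows for several shocks within a patient.

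**Cost.** Mostly wording. The shock sequence already fixes which shocks carry pressure, but section 3.2 records operator shock only as a post-procedural complication, so the CRF must also note at which shock it occurred. The conclusion would change from a statement about significance to one that the risk is no higher than a given percentage. With 154 patients per arm that percentage cannot fall below 2.4% for the intervention arm (two-sided 95%), so an acceptable rate below this could not be met.
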